7. STATISTICAL ANALYSIS

Sample size calculation

Using a sample size equation for longitudinal clustered samples,⁸⁴ a power analysis was conducted for the **primary outcome: percent weight change at week 72**. Estimated group means, attrition rate, intraclass correlation (ICC), and variances were derived from data from prior studies

conducted at our Center.⁷² Specifically, we predict a 72-week weight loss of 9% in the stigma + BWL group and 5% in the BWL group, with expected standard deviations of 7%.⁷² Based on these estimates, a baseline sample size of 104 participants (52 per group), assuming a 20% attrition rate, an ICC of .80, and 4 assessment points, will give us 80% power to detect a between-treatment group difference at week 72 of 4% (effect size: 0.57) to be significant at alpha = 0.05. The power analysis was conducted using PASS v14. All secondary outcomes will be considered exploratory and will provide valuable findings that will help to inform larger studies. This study has not been powered to detect differences in changes in physical activity, cardiometabolic outcomes, or psychosocial variables.

Analysis plan

Data quality and integrity will be checked by assessing the data for missing and out-of-range values with basic statistical procedures, including univariate statistics and visual graphical displays (e.g., scatter plots). We will investigate all questions of data quality and integrity prior to performing any statistical modeling. To test the adequacy of randomization, preliminary analyses will include a comparison of all participant demographic and baseline characteristics by randomized treatment groups (t-tests or Wilcoxon rank sum tests for continuous variables and Chi-Square test or Fisher's Exact test for categorical data). If imbalances are observed, the relevant variables will be included as covariates in the final analyses.

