All data will be analyzed with a modified intention-to-treat principle. Participants who attend at least one group meeting (i.e., receive a dose of treatment) will be included in the analyses; participants who do not attend a single group meeting will not be included in the analyses. Analyses will be two-tailed with a significance level of 0.05, and will be conducted using SPSS version 24.0 or SAS version 9.4. To assess the primary outcome of percent weight change by treatment group, a mixed effects model will be fit with Treatment Group (*stigma+BWL, BWL*) as a between subjects factor and Time (*Weeks 20, 46, 72*) as a categorical within-subjects factor. We will use the group x time interactions with the time main effect to estimate and test treatment group differences at each time point, with the 72-week time point as our primary test. In fitting a mixed effects model with residual maximum likelihood (REML), a variance-covariance structure must be selected. The criteria for selecting the best form of the variance-covariance structure will be based on criteria such as the Akaike's Information Criterion (AIC). We will include as baseline covariates any variables that differ significantly between the treatment groups at baseline and show significant relationships with the outcome. The results from the mixed model will be summarized by mean(SE) for each treatment group at each time point. Residual analyses will be conducted to check for outliers and influential points and violations in the normality assumption. If violations are detected, variance-stabilizing transformations will be considered. Logistic regression will be used to test for between-group differences in categorical weight loss ($\geq 5\%$ and $\geq 10\%$ of initial body weight) at weeks 72, 46, and 20.

The second aim of assessing changes in physical activity and self-efficacy, and the secondary aims of comparing changes in cardiometabolic risk factors and psychological well-being (including WBI), will be analyzed using the same methods as described above for the mixed effects model used for the primary aim. Changes in all outcomes will be summarized by mean(SE) for each treatment group at each time point. Logistic regression will be used to test for between-group

differences at weeks 20, 46, and 72 in the percentage of participants who have remitted from elevated WBI, as indicated by no longer having a score of 4 or above.

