This study will consider death, pregnancy, bariatric surgery, amputation, and other major medical events or procedures that require a participant to terminate treatment as "censoring events." For primary analyses, participants experiencing these events will be censored at the last measured weight before the event occurred. As discussed above, the primary analysis techniques being employed (i.e., linear mixed models) can accommodate incomplete participant response profiles, so these participants will still be included in the analyses. Additional sensitivity analyses may be conducted in which data will be censored due to other factors that directly affect weight (e.g., change of medication that affects weight, receipt of additional weight-related treatment, change in smoking status, or other major medical changes that occur within 3 months of an assessment visit).

Additional analyses may be conducted to explore potential effects of cohort, time of group meeting, and group leader on weight loss and changes in WBI. Analyses may also explore potential differences in attendance between groups and the effects of attendance on weight loss and changes in WBI.

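### The logistic analyses of ≥5%/≥10% weight loss and WBI remission carry no missing-data rule, so modified-ITT inclusion is not secured for these exploratory endpoints

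*Combined protocol and SAP*

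**What the plan says.** Section 7 (Analysis plan) sets the population for everything: "All data will be analyzed with a modified intention-to-treat principle". It adds: "Participants who attend at least one group meeting (i.e., receive a dose of treatment) will be included in the analyses".

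The continuous outcomes go to a mixed effects model over weeks 20, 46 and 72. Two sets of binary outcomes are treated separately. For loss of at least 5% and at least 10% at weeks 72, 46 and 20: "Logistic regression will be used to test for between-group differences in categorical weight loss". For WBI remission, meaning a Weight Bias Internalization Scale (WBIS) score that has fallen below 4, logistic regression tests for between-group "differences at weeks 20, 46, and 72 in the percentage of participants who have remitted from elevated WBI".

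The only text on incomplete data comes in the paragraph on censoring events: "the primary analysis techniques being employed (i.e., linear mixed models) can accommodate incomplete participant response profiles". The sensitivity analyses offered there are optional and would censor more data.

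Two statements under Sample size calculation in section 7 bear on size and weight. The calculation is made "assuming a 20% attrition rate", and "All secondary outcomes will be considered exploratory". Section 6.3 lists categorical weight loss as a secondary outcome and describes WBI remission under its secondary outcomes.

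**The concern.** The promise of inclusion covers all data, but the mechanism that would deliver it is named only for linear mixed models. A participant with no weight or WBIS score at a given week has no 0/1 outcome, and ordinary logistic regression leaves that person out unless the plan provides otherwise. No imputation, non-responder rule or repeated-measures binary model is given. Nor does the plan say how a participant censored after a medical event is to be classed as a responder.

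Three things are at stake. The week-72 mean and the week-72 responder proportion may describe different sets of participants. The responder analysis throws away week-20 and week-46 values, which carry information about week 72 even when missing-at-random holds exactly. And with no rule written down, the denominator could be chosen after the data are seen.

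**Working it through.** **1. The plan's own figure.** Inputs from section 7: difference 4 points, SD 7, 4 assessments, ICC .80, two-sided 0.05, 80% power, 20% attrition. Per arm, n = 2[SD(z.975 + z.80)/δ]² × [1 + (m − 1)ρ]/m = 2[7(1.960 + 0.842)/4]² × (1 + 3 × .80)/4 = 48.07 × .85 = 40.9, so 41. Then 41/.80 = 51.25, so 52 per arm and 104 in total. The stated 104 reproduces. No responder rate or power is stated for the logistic endpoints.

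**2. Who is left out.** 104 × .20 = 20.8, so about 21 participants would by default be absent at week 72 and about 83 present (41 to 42 per arm).

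**3. Week-72 responder rates if everyone were measured.** Assuming normal percent loss with the plan's means (9 and 5) and SD 7:
- ≥5%: 1 − Φ((5 − 9)/7) = .716 and 1 − Φ(0) = .500. Odds ratio (.716/.284)/(.500/.500) = 2.52.
- ≥10%: 1 − Φ(1/7) = .443 and 1 − Φ(5/7) = .238.

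**4. Range without a dropout model.** Take .716 and .500 as the completer ≥5% rates. With 20% missing in each arm, overstatement = .20 × (completer rate − dropout rate). For stigma + BWL and BWL it is:
- 14.3 and 10.0 points if no dropout responds
- 7.2 and 5.0 if dropouts respond at half the completer rate
- 0 if at the same rate
- −2.9 and −2.0 if at 1.2 times that rate

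**5. Dropout that is missing at random.** My assumptions: week-46 means of 9 and 6.5; correlation .80 between week-46 and week-72 loss (the plan's ICC); dropout after week 46 with logit = a − b × (week-46 loss), the intercept a shared by both arms and set to give 20% overall. The completer rate is ∫r(y)q(y)f(y)dy / ∫r(y)f(y)dy. Here f is the normal density of week-46 loss, r is the probability of staying, and q(y) = 1 − Φ((5 − μ72 − .8(y − μ46))/4.2), with 4.2 = 7√(1 − .64). Results for ≥5%:

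| Slope b | Completer rates (stigma + BWL / BWL) | Overstatement, points | Odds ratio |
|---|---|---|---|
| −0.1 | .681 / .462 | −3.5 / −3.8 | 2.48 |
| 0 | .716 / .500 | 0 / 0 | 2.52 |
| 0.1 | .751 / .545 | 3.5 / 4.5 | 2.52 |
| 0.2 | .775 / .580 | 5.9 / 8.0 | 2.49 |
| 0.3 | .789 / .602 | 7.3 / 10.2 | 2.47 |

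With correlation .5 and slope 0.2, the completer rates are about .75 and .55.

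**6. Dropout that works differently by arm.** Same set-up, 20% overall, slope 0.2 in one arm and 0 in the other. The completer odds ratio is about 3.1 if only stigma + BWL dropout depends on weight loss, and about 2.1 if only BWL dropout does, against 2.52.

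**7. Counting missing as non-response (≥5%).** At slope 0.2 the rates are .644 and .446, so the odds ratio is (.644/.356)/(.446/.554) = 2.25. At slope 0 they are .80 × .716 = .573 and .80 × .500 = .400, giving (.573/.427)/(.400/.600) = 2.01, where completers give 2.52.

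**8. Precision, ≥5%, slope 0.2.** SE of the log odds ratio = √Σ1/[n p(1 − p)].
- Completers, about 41.6 per arm: √(1/(41.6 × .775 × .225) + 1/(41.6 × .580 × .420)) = .49.
- All 52 per arm observed: √(1/(52 × .716 × .284) + 1/(52 × .25)) = .41.
- Multiple imputation must fall between; in simulation it gave about .44, with rates restored to about .72 and .50.
- Simulated power was about 45% for completers and 55% after imputation. The normal approximation agrees: Φ(.912/.49 − 1.96) = .46 and Φ(.925/.44 − 1.96) = .56.

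**The case against.** The strongest reply is that the plan tests a contrast, logistic regression estimates an odds ratio, and step 5 shows that odds ratio hardly moving (2.47 to 2.52 against 2.52) when dropout follows the same rule in both arms. That stands. The ≥5% risk difference does fall at slope 0.2, from 21.6 to 19.5 points, but the plan does not analyse on that scale. For ≥10% it does not fall at all (about 21 points either way).

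It is also true that the text never says missing participants will be dropped or that a separate model is fitted at each week. Dropping is the default of a method left unspecified. Nor do the documents say how dropouts fare, so the slope and the week-46 means are assumptions. Section 6.2 allows remote weights and online questionnaires during the pandemic, so a missed clinic visit need not mean a missing value, and the 20% is a planning figure. The endpoints are exploratory.

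What the reply does not remove is the gap itself. The statement that such models "can accommodate incomplete participant response profiles, so these participants will still be included in the analyses" cannot be carried over to logistic regression. Equal dropout mechanisms in the two arms cannot be taken for granted when the interventions differ, and the precision loss arises even when the odds ratio is unbiased.

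**Conclusion.** The point holds as a gap in the plan: modified-ITT inclusion is promised for all data but not secured for the responder and remission endpoints, with about 21 of 104 absent by default at week 72. A better method is available at little cost, so the change should be made.

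The size depends on assumptions. Completer ≥5% rates would be too high by about 3 to 10 points for slopes of 0.1 to 0.3. The ≥5% odds ratio is close to right under common dropout, and about 2.1 or 3.1 instead of 2.52 when dropout depends on weight loss in one arm only. The standard error is about .49 where imputation would give about .44. No remission rate is stated, so no figure can be given for WBI.

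Three stronger readings should be resisted. A reader might infer that completer rates must overstate response; the documents contain no data on dropouts, and the error is zero or negative if dropouts did as well or better. A reader might infer that the between-arm comparison is necessarily distorted; under a common dropout mechanism it is not, on the scale the plan uses. And a reader might infer that the trial's main conclusion is at risk; the primary mixed-model test and the sample size do not depend on these analyses.

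**What to change.** Add a missing-data rule for the binary endpoints to section 7:
- For every modified-ITT participant, multiply impute missing percent weight change at weeks 20, 46 and 72 from a model with the primary mixed model's terms and the values at the earlier visits. Impute WBIS in the same way.
- Dichotomize the imputed values at 5%, 10% and the WBIS cutoff of 4, run the planned logistic regression in each imputed set, and pool the results.
- State that values after a censoring event are treated as missing and imputed by the same rule.
- If missing is also counted as non-response, label it a sensitivity analysis and note that it can bias the odds ratio more than the completer analysis does (step 7).

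The cost is a few sentences in the plan and modest extra programming. The result relies on missing-at-random given the observed visits, as the primary model already does, and the reported responder and remission rates may come out less favourable.

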3. SPECIFIC AIMS

Aim 1. To test, in a randomized controlled trial, the effects of a novel 29-session cognitive-behavioral weight stigma intervention, combined with BWL (in comparison to standard BWL alone), in producing long-term weight loss (at week 72) in a total of 104 individuals with obesity who have experienced weight stigma.

H1: Patients who receive the stigma + BWL intervention will achieve significantly greater weight loss at week 72 than patients assigned to standard BWL (9% and 5% of initial weight, respectively).

Aim 2. To assess whether the stigma + BWL intervention significantly increases physical activity and self-efficacy (as compared with BWL alone).

H2: Patients who receive the stigma + BWL intervention will achieve significantly greater levels of physical activity and exercise self-efficacy at weeks 20, 46, and 72 than patients assigned to standard BWL.

Secondary Aims

3. To compare changes in cardiometabolic risk factors (e.g., metabolic syndrome) in patients assigned to the stigma + BWL intervention versus BWL alone.

H3: Patients who receive the stigma + BWL intervention will achieve significantly greater reductions in cardiometabolic risk at week 72 than patients assigned to standard BWL.

4. To evaluate changes in psychological distress (e.g., WBI) in the stigma + BWL intervention compared to BWL alone.

H4: Participants who receive the stigma + BWL intervention will have greater reductions in WBI and psychological distress at weeks 20, 46, and 72 than participants receiving BWL alone.

5. To compare short-term weight change in patients assigned to the stigma + BWL intervention versus BWL alone.

H5: Participants who receive the stigma + BWL intervention will achieve significantly greater weight loss than patients assigned to standard BWL at weeks 20 and 46.

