Lifestyle Efficacy (WEL),⁷¹ which measure individuals' confidence in their ability to overcome barriers to exercising and controlling their weight. Greater physical activity by objective and self-report assessment is expected in the stigma + BWL intervention vs. BWL alone group at weeks 20, 46, and 72. Based on prior research,¹³ we predict that participants in the stigma + BWL group will engage in approximately 250 min/wk of physical activity at week 72, as compared to approximately 150 min/wk in the BWL alone group, thus contributing to the 4% difference in weight loss at week 72.

Cardiometabolic risk. Blood pressure, waist circumference, and blood samples (measures: triglycerides, cholesterol, and glucose) will be obtained at screening and weeks 20 and 72 to assess changes in cardiometabolic risk factors, particularly in the components and diagnosis of metabolic syndrome. Blood pressure also will be assessed at randomization. Blood pressure will be measured using an automated Dinamap monitor (Johnson & Johnson, XL model 9300) at three, 1-minute intervals after \geq 5 minute rest, using measures described previously.⁷² Waist circumference will be measured (to the nearest 0.1 cm) in duplicate with flexible tension-controlled measuring tape midway between the iliac crest and lowest rib. Blood samples will be drawn after an overnight fast to obtain plasma glucose levels and a lipid panel (triglycerides and HDL cholesterol), along with inflammatory markers of cardiometabolic risk (e.g., C-reactive protein). Samples will be sent to Quest Diagnostics (Horsham, PA) for analysis. Additionally, the study nurse practitioner or physician will review current medication use. Improvements in triglycerides, HDL cholesterol, and glucose are expected at week 20 in both treatment groups because of acute weight loss and calorie restriction. Due to higher levels of physical activity, greater weight loss, and reduced WBI, the magnitude of improvement is expected to be greater in the stigma + BWL intervention vs. BWL alone group at week 72.

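### The metabolic syndrome diagnosis is yes/no, but the only analysis covering it is a linear mixed model of change; modelling it as a binary outcome with baseline diagnosis as a covariate would fit better and cost almost nothing

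*Combined protocol and SAP*

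**What the plan says.** - **Aim 3 (Section 3)** gives metabolic syndrome as its only example: "To compare changes in cardiometabolic risk factors (e.g., metabolic syndrome".
- **Section 6.3, Cardiometabolic risk**, says that blood pressure, waist and blood samples "will be obtained at screening and weeks 20 and 72 to assess changes in cardiometabolic risk factors". It adds that the interest lies "particularly in the components and diagnosis of metabolic syndrome". So the outcome set holds continuous components and a yes/no diagnosis. Sections 4.1 and 6.2 confirm that no blood is drawn at week 46.
- **Section 7, Analysis plan**, handles the secondary aims as a group: "comparing changes in cardiometabolic risk factors and psychological well-being (including WBI), will be analyzed using the same methods as described above". The model referred to is fitted by REML, with weeks 20, 46 and 72 as the time factor, residual checks for normality, and variance-stabilising transformations as the remedy. The paragraph on censoring events calls it a linear mixed model. All outcomes are to be summarised by mean (SE) of change.
- **Covariates.** A baseline variable enters the model only if the arms differ significantly on it and it is related to the outcome.
- **Logistic regression** is named for two outcomes: weight loss of at least 5% or 10%, and remission from elevated WBI. The metabolic syndrome diagnosis is not mentioned in Section 7.
- **Status.** Section 7 calls secondary outcomes exploratory and states that the study is not powered for cardiometabolic outcomes.

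**The concern.** Applied as written, a 0/1 diagnosis becomes a change score of -1, 0 or +1, modelled with normal errors. Three features of the stated method do not suit it. No transformation can make a three-valued variable normal. The time factor has a level, week 46, at which the diagnosis is not measured. A mean (SE) of change offsets resolved cases against new ones and does not show how many people have the diagnosis at week 72 given where they started.

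The covariate rule adds a fourth. Baseline diagnosis would enter the model only after a chance imbalance, so the usual analysis would be an unadjusted change score. If baseline and week-72 status are only moderately correlated, subtracting baseline adds noise. At stake is the precision and readability of one Aim 3 result that, according to Section 7, should help to inform larger studies.

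**Working it through.** **The plan's own figure.** None is given for metabolic syndrome. The sample size is for percent weight change. Its inputs are "a baseline sample size of 104 participants (52 per group), assuming a 20% attrition rate, an ICC of .80, and 4 assessment points". The stated result is that these "will give us 80% power to detect a between-treatment group difference at week 72 of 4% (effect size: 0.57". With SD 7% and a repeated-measures factor of [1 + 3 × 0.80]/4 = 0.85:

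n = 2 × (1.960 + 0.842)² × 49 × 0.85 / 16 = 40.86 per arm; 40.86 / 0.80 = 51.08, rounded up to 52.

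So 104 reproduces. What carries over is the number expected at week 72: 52 × 0.80 = 41.6, taken as 42 per arm. The test level is also from the plan: "Analyses will be two-tailed with a significance level of 0.05".

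**Assumptions, none from the documents.** Baseline prevalence 50% in both arms. Week-72 prevalence 45% (BWL) against 20% (stigma + BWL), or 45% against 35%. Baseline and week-72 status are cut from a bivariate normal with correlation r from .5 to .95.

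**Is the change-score contrast biased?** With common baseline prevalence p0 under randomisation, (pT - p0) - (pC - p0) = pT - pC. It estimates the week-72 risk difference.

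**Precision, one case by hand (45% against 20%, r = .7).** The covariances of baseline and week-72 status are 0.1222 (BWL) and 0.0792 (stigma + BWL).

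- *Change score.* Variance is p0(1-p0) + p1(1-p1) - 2cov. BWL: 0.25 + 0.2475 - 0.2444 = 0.2531. Stigma + BWL: 0.25 + 0.16 - 0.1584 = 0.2516. SE = √[(0.2531 + 0.2516)/42] = 0.1096. 0.25/0.1096 = 2.28, and power is about Φ(2.28 - 1.96) = 63%.
- *Baseline-adjusted.* Slope b = [(0.1222 + 0.0792)/2]/0.25 = 0.403. Variance is p1(1-p1) - 2b·cov + b²p0(1-p0). BWL: 0.2475 - 0.0985 + 0.0406 = 0.1896. Stigma + BWL: 0.16 - 0.0638 + 0.0406 = 0.1368. SE = √[(0.1896 + 0.1368)/42] = 0.0882. 0.25/0.0882 = 2.84, and power is about Φ(0.88) = 81%.
- *Unadjusted week-72 status.* SE = √[(0.2475 + 0.16)/42] = 0.0985. 0.25/0.0985 = 2.54, and power is about Φ(0.58) = 72%, whatever r is.

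**Simulation, 42 per arm, 45% against 20%** (a point or two below the normal approximation):

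| Analysis of the diagnosis | r = .5 | .7 | .85 | .95 |
|---|---|---|---|---|
| Linear, change score | 52% | 62% | 73% | 83% |
| Binary, stratified by baseline (Mantel-Haenszel) | 74% | 79% | 86% | 91% |
| Linear, adjusted for baseline | 75% | 79% | 86% | 91% |
| Binary, unadjusted | about 70% | about 70% | about 70% | about 70% |

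Baseline adjustment gains 22 points at r = .5 and 8 points at r = .95. For 45% against 35%, power is about 13-25% for the change score and 16-28% with adjustment: low either way.

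**Type I error.** With equal week-72 rates, the change-score test rejected in 3.9% to 5.4% of runs.

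**Reading the table.** The second and third rows are the same to within a point, so the binary family adds no power. The gain comes from conditioning on baseline. Unadjusted logistic regression beats the change score at low correlation, but loses to it once status is very stable.

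**Limits.** These are single-visit comparisons among completers, standing in for the week-72 contrast of a repeated-measures model. Section 6.2 lets remote assessments replace in-person visits during the pandemic. Remote visits have no blood test or blood pressure, so fewer than 42 per arm may have a diagnosis at week 72.

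**The case against.** The strongest reply is that this is an omission, not a misassignment. Section 7 routes cardiometabolic risk factors as a group and never names the diagnosis. The continuous components suit the planned model, and the authors gave logistic regression to the yes/no efficacy outcomes they did name. That reading is fair, but it leaves the diagnosis with no stated analysis, and the same sentence cures both.

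The plan does not ignore baseline: a change score uses it by subtraction, and the covariate rule can admit it. That also stands. The complaint is inefficiency, not discarded data.

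Every rate in the working is assumed, and a 25-point difference is large. This stands too: with a 10-point difference the practical gain is three or four points of power.

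A logistic model with an interaction and baseline diagnosis may meet sparse cells. In the 45% against 20% scenario, between 16% (r = .5) and 79% (r = .85) of simulated trials had no stigma-arm case at week 72 among participants negative at baseline. The fix therefore needs a fallback.

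A reader might infer that the Gaussian model is itself invalid or loses power. The calculations do not support that: type I error holds, the contrast is a risk difference, and the adjusted linear model matches the binary one. A reader might also infer that H3 stands or falls on this comparison. Section 3 does not say so: H3 concerns cardiometabolic risk in general, and metabolic syndrome is an example in the aim.

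**Conclusion.** The point holds as a minor improvement. For the metabolic syndrome diagnosis, the analysis in Section 7 is valid but poorly fitting and inefficient: its normality checks, week-46 level and mean-change summaries do not suit the outcome, and baseline status is used only by subtraction. Under the assumed large difference the cost is roughly 8 to 22 points of power; under the smaller one it is about 3. These sizes rest wholly on assumed prevalences, correlation and 42 evaluable participants per arm. Only the mismatch between outcome type and stated method comes from the documents. Because the outcome is exploratory and the trial claims no power for it, the primary conclusion is unaffected.

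**What to change.** Add to the analysis plan in Section 7:

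- Metabolic syndrome diagnosis at weeks 20 and 72 is analysed as a binary outcome (logistic or GEE), with arm, visit, arm × visit and baseline diagnosis as a covariate, whether or not the arms differ on it at baseline.
- If cells are too sparse for a stable fit, use a Mantel-Haenszel analysis stratified by baseline diagnosis, or a penalised logistic model.
- Report the week-72 risk difference or odds ratio with a 95% confidence interval, and the number with the diagnosis in each arm at each visit.
- Keep the linear mixed model for the continuous components, with weeks 20 and 72 as the time levels for those not measured at week 46.

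Extending the plan's logistic regression to this outcome without baseline diagnosis would not reliably bring the gain. The cost is a few lines of text, no new data, and a rule for the few participants who may lack a baseline diagnosis.

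### The continuous outcomes of Aims 2 to 4 have no prespecified adjustment for their own baseline, and the dependent variable is not written out; this costs precision but does not bias the comparison (minor).

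*Combined protocol and SAP*

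**What the plan says.** Section 7 (Analysis plan) sets out the primary model for percent weight change. Treatment group is a between-subjects factor, and time, with levels at weeks 20, 46 and 72, enters "as a categorical within-subjects factor". Group differences at each visit come from the group-by-time terms.

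The outcomes of the later aims are then attached to that model. The paragraph opens with "The second aim of assessing changes in physical activity and self-efficacy", adds the cardiometabolic and psychological outcomes, again described as changes, and says that all of these "will be analyzed using the same methods as described above for the mixed effects model used for the primary aim". It closes with "Changes in all outcomes will be summarized by mean(SE) for each treatment group at each time point". Section 3 words H2 differently: the stigma + BWL group "will achieve significantly greater levels of physical activity and exercise self-efficacy at weeks 20, 46, and 72".

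Two sentences in Section 7 govern covariates. After the baseline comparison of the arms: "If imbalances are observed, the relevant variables will be included as covariates in the final analyses". In the model description, the covariates are "any variables that differ significantly between the treatment groups at baseline and show significant relationships with the outcome".

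Baseline values are collected. Section 6.2 schedules activity monitoring and questionnaires at baseline and at the three follow-up assessments. Section 6.3 places the WBIS and the cardiometabolic measures at screening. Section 7 declares all secondary outcomes exploratory and says the study is not powered for activity, cardiometabolic or psychosocial changes.

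**The concern.** Percent weight change is already scaled by baseline weight, so a model without a separate baseline term is understandable for the primary outcome. That reasoning does not carry over to activity minutes, self-efficacy scores, WBIS, blood pressure or lipids. For these, a raw change score brings the full baseline measurement error into the outcome, and a raw follow-up level makes no use of the baseline. Under randomization, both target the same between-arm difference as a baseline-adjusted model, usually with a larger standard error.

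What is at stake is the precision of estimates that Section 7 says are meant to inform larger studies. There is also a gap in specification: an analyst could fit either changes or levels and claim to have followed the plan.

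**Working it through.** **The plan's own figure.** The inputs, from Section 7, are: difference 4, SD 7, ICC 0.80, 4 assessment points, two-sided alpha 0.05, power 80%, attrition 20%. The repeated-measures formula gives n per arm = 2 × (1.960 + 0.842)² × 7²/4² × [1 + 3 × 0.80]/4 = 48.07 × 0.85 = 40.9, so 41. Then 41/0.80 = 51.25, so 52 per arm and 104 in total. The stated size reproduces. It belongs to percent weight change; no size or power is given for Aims 2 to 4.

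**What the model contains.** Baseline is not among the time levels, so it is not a response. It is not a named covariate. It can enter only through the two imbalance rules.

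**Variance under each reading.** Assumptions: one follow-up visit, the same SD s at baseline and follow-up, correlation r. The documents give no r for these outcomes, so a range is shown.
- Raw change: 2s²(1 − r)
- Raw level: s²
- Baseline-adjusted: s²(1 − r²)
- Adjusted relative to change: (1 + r)/2. Adjusted relative to level: 1 − r².

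The detectable difference is in outcome SDs, at 80% power with 52 × 0.8 = 41.6 completers per arm. It equals 2.80 × √(2/41.6) = 0.614, multiplied by √[2(1 − r)] for change or √(1 − r²) for adjusted.

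| r | Adjusted / change | Adjusted / level | Detectable difference, change vs adjusted | Adjusted power where raw change has 80% |
|---|---|---|---|---|
| 0.3 | 0.65 | 0.91 | 0.73 vs 0.59 | about 94% |
| 0.5 | 0.75 | 0.75 | 0.61 vs 0.53 | about 90% |
| 0.7 | 0.85 | 0.51 | 0.48 vs 0.44 | about 86% |
| 0.8 | 0.90 | 0.36 | 0.39 vs 0.37 | about 84% |

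**Unequal SDs.** With baseline SD s0 and follow-up SD s1, Var(change) − Var(adjusted) = (s0 − r·s1)², and Var(level) − Var(adjusted) = (r·s1)². Neither can be negative, so adjustment never loses precision apart from its degrees of freedom. The size does depend on k = s0/s1: Var(change)/Var(adjusted) = (1 + k² − 2rk)/(1 − r²).
- r = 0.5: k = 1 gives 1.00/0.75 = 1.33; k = 0.7 gives 0.79/0.75 = 1.05; k = 0.6 gives 0.76/0.75 = 1.01.
- r = 0.3: k = 1 gives 1.40/0.91 = 1.54; k = 0.6 gives 1.00/0.91 = 1.10.

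The k values are assumptions. Values below 1 are plausible where Section 5.2 truncates the baseline: WBIS of 4 or above, and less than 150 minutes per week of structured activity.

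**Does the covariate rule make up the loss?** The stricter rule (significant baseline difference and significant relation to the outcome) was simulated with 42 per arm, equal SDs and 20,000 runs per r. The outcome's baseline entered in 4.9%, 4.9% and 4.2% of runs at r = 0.3, 0.5 and 0.8. Variance fell by about 9%, 7% and 3%, against 35%, 25% and 10% when baseline is always included. The rule recovers between a quarter and a third of the available gain.

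**The case against.** The case for leaving the plan alone has real weight.

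- These outcomes are declared exploratory and unpowered, and a change-score analysis is unbiased under randomization. This stands, and it sets the severity.
- The plan does allow baseline variables into the model. A reader might infer that the outcome's baseline is excluded outright; the two rules in Section 7 show otherwise. The accurate statement is that it is not prespecified and depends on an observed imbalance.
- A reader might take the sentence about mean (SE) summaries as proof that raw change is modelled. It concerns reporting only. The carry-over to the primary-aim methods, together with the word changes, makes raw change the natural reading, but it remains an inference.
- The only correlation in the documents is the ICC of 0.80, given for the primary outcome. If it applied here, the variance ratio would be 0.90 and the raw-change standard error about 5% larger (1/√0.90 = 1.054). The loss could therefore be modest, and for WBIS the truncated baseline could shrink it further.
- The conflict between changes and levels is slight, since only H2 uses the second word.

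None of this gives a reason to leave the baseline term out. The imbalance rules rarely bring it in, and including it costs almost nothing.

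**Conclusion.** The point holds as a minor improvement in efficiency and specification. For the continuous outcomes of Aims 2 to 4, the dependent variable should be stated and the outcome's own baseline prespecified. With equal SDs, adjustment reduces the raw-change variance by 35%, 25%, 15% and 10% at r = 0.3, 0.5, 0.7 and 0.8. It reduces it by less where the baseline SD is below the follow-up SD, and by nothing where s0 = r·s1. Against a raw-level analysis the reduction is r². Both r and the SD ratio are assumptions, and the formulas treat a single visit without modelling the missing data.

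Two stronger conclusions are not supported. A reader might convert the variance ratio into extra participants and call the trial too small for these aims, but the 104 was sized for percent weight change and there is no target for Aims 2 to 4 to miss. A reader might also conclude that the planned comparisons are biased; the form of the analysis gives no such bias under randomization.

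Section 6.2 describes handing out accelerometers after allocation at the randomization visit. Whether baseline activity is recorded before the arm is known is a separate procedural question and is not part of this point.

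**What to change.** In the Section 7 paragraph on the second and secondary aims:

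1. Name the dependent variable for each continuous outcome (follow-up value or change from baseline) and align H2 with it.
2. Include the outcome's own baseline value and its interaction with visit as prespecified fixed terms, whatever the baseline comparison shows. Alternatively, fit a constrained longitudinal model with baseline as the first time point and a common baseline mean in both arms. For the blood markers the follow-up visits are weeks 20 and 72 only.
3. Report the adjusted between-arm difference at each visit with a 95% CI, alongside the planned group summaries.

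With the baseline term in the model, change and follow-up value give the same treatment contrast, so the difference between changes and levels no longer affects the result. The cost is SAP wording and one or a few degrees of freedom per model; the baseline measurements are already scheduled.
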